### *Discontinuation of Study Product Use and Withdrawal From the Study*

Participants have the right to decline study procedures for any reason and at any time during the study with no penalty. If a participant decides to discontinue study procedures, including AA-ORS or placebo administration, this will be recorded as a study deviation and the reason will be clearly documented.

Participants have the right to withdraw from the study at any time and for any reason, without penalty. If a caregiver does not wish to remain in the study and/or decides to stop administering the solution altogether to his/her child, the participant can choose to withdraw consent and be withdrawn from the study. That decision will be documented, and study staff will attempt to schedule a final post-dosing IDI and medical examination as soon as possible to confirm the welfare of the child.

The principal investigator and site PI may, at their discretion, withdraw a subject from continuing in the study if it is considered to be in the participant's best interest to do so, or if the participant is not willing or able to comply with the study requirements. The reason for withdrawal will be documented. Withdrawn subjects will not be replaced in the study. The data collected before withdrawal will be analyzed.

Withdrawal from further study product administration may be at the discretion of the PI or site PI, in consultation with the study pediatrician if it is in the interest of the subject. In addition, participants will be withdrawn from further study product administration for the following reasons:

- Ineligibility (either arising during the study or retrospectively having been overlooked at enrollment).
- Significant protocol deviation.
- Significant noncompliance with the study product regimen or study requirements.
- Significant weight loss: if a child loses more than 5% of his or her body weight from that measured at enrollment, the child will be withdrawn from the study. The study team will refer the withdrawn child and caregiver to his or her primary health care provider or CGH, as appropriate.
- An AE (including intercurrent illness, diseases, or medical treatment) that requires discontinuation of study product use or results in inability to continue to comply with study procedures (Appendix 2). The study team will refer anyone that develops an acute illness during the study to his or her primary health care provider or CGH, as appropriate.

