#### xi. Data management and analysis plan

##### *Data Management Procedures*

IDI data will be analyzed qualitatively, using transcripts and notes to identify key themes and topics.

DOs will be manually coded and analyzed to identify the time taken to drink up to 237 ml of AA-ORS, ease of administration, and visible signs of palatability.

Quantitative clinical data focused on demographics, anthropometrics, AEs, product volume consumed daily, plasma/serum micronutrients, metabolic markers (acylcarnitine profile), EED markers (gut dysfunction and growth hormone resistance), and systemic inflammation will be collected on standardized forms or exported to computerized databases by RAs and laboratory workers. Form data will be double entered into a password-protected Microsoft Access database by RAs blinded to the supplementation assignment (AA-ORS vs. placebo). After entering all data and resolving inconsistencies, the data set will be locked.

All data will be stored on password-protected computers in PATH offices. Only members of the study team will have access to the raw transcripts, CRFs, and consent forms in a locked filing cabinet.

*Data Analysis Procedures***DEFINITIONS OF POPULATIONS TO BE ANALYZED**

**The intention-to-treat population** will include all participants who are assigned AA-ORS or placebo regimen and receive at least one dose, regardless of whether he/she completes the full 14-day regimen (or misses dose[s] of study product for a medical reason such as vomiting). The first primary (safety), secondary (caregiver acceptability), and exploratory (biomarker) analyses will be performed using this population.

**The per-protocol population** will include all participants who are assigned a regimen with no major protocol violations that are determined to potentially interfere with the ad-libitum dosing of the study solution(s) (i.e., early withdrawal or product discontinuation, etc.). This population will serve as the primary analysis population for the volume consumption and consumption factor endpoint. As the primary objective is to accurately estimate the average daily volume consumed in the full sample (AA-ORS + placebo), it is critical that all subjects in the population have completed a full dosing regimen.

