**STUDY ENDPOINTS TO BE ANALYZED AND ANALYTICAL METHODOLOGY**

**Primary:** AEs and SAEs through 21 days of follow-up, and changes to dietary and digestive habits through day 14 of follow-up.

*For AEs and SAEs that occur within 21 days of enrollment, statistical comparisons will be made between the AA-ORS and the placebo solution groups using Fisher's exact test. Changes to feeding habits (normal, less frequent/less volume, more frequent/more volume), diarrhea (1–2, 3–4, 5–7, or 7+ events in 24 hours), and vomiting (none, 1, 2–5, > 6 events in 24 hours, or hospitalization) will be made using chi-square tests.*

**Primary:** Average daily product volume consumed through 14 days of follow-up, time trends in daily volume consumed, and factors that influence children's willingness and ability to ingest the product as intended.

*The average daily volume (and statistical distribution) of solution consumed by children over the 2-week period will be calculated. These descriptive data will be pooled from AA-ORS and placebo arms as the solutions are designed to taste the same. Lowess curves will be used to describe trends in volumes consumed, and linear mixed effects models will be used to test for an association between day of follow-up and product volume consumed. We will use linear regression to identify factors (e.g., child weight, length, and age) associated with a child's average daily intake.*

**Secondary:** Key factors that influence caregivers' willingness to have the product used by their children, and their perception of their children's response to its consumption.

*These qualitative analyses will use ATLAS.ti software to identify and group key themes and topics from IDI notes.*

**Exploratory:** Average plasma/serum concentrations of metabolic, gut dysfunction, systemic inflammation, and micronutrient biomarkers at baseline and day 15 of follow-up.

*Metabolic, EED, systemic inflammation, and micronutrient marker data collected at baseline will be pooled across intervention groups and used to generate descriptive statistics for the study population. The same descriptive statistics will be generated for day 15 of follow-up. Paired student's t test will be used to compare these continuous parameters between baseline and day 15 of follow-up.*

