#### ISSUES WITH MISSING DATA AND MULTIPLICITY

We will analyze whether there is differential missingness or loss to follow-up by supplementation arm for the primary endpoints. No imputation of missing outcome data is planned. We will adjust the significance level for multiple comparisons by using the Benjamini-Hochberg method to control for the false discovery rate for related hypotheses.

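### The primary analysis of volume, trend and consumption factors is restricted to children who complete the regimen, and no all-dosed analysis of this endpoint is specified

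*Combined protocol and SAP*

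**What the plan says.** Section C.xi (Definitions of populations to be analyzed) sets up two populations. The intention-to-treat population is every child assigned a regimen who receives at least one dose. Its uses are listed: "The first primary (safety), secondary (caregiver acceptability), and exploratory (biomarker) analyses will be performed using this population". Volume is not among them.

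The per-protocol population excludes children with major violations "determined to potentially interfere with the ad-libitum dosing of the study solution(s) (i.e., early withdrawal or product discontinuation, etc". The plan then states: "This population will serve as the primary analysis population for the volume consumption and consumption factor endpoint". The reason given is that the average daily volume over both arms should be estimated accurately, for which "it is critical that all subjects in the population have completed a full dosing regimen".

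The endpoint section of C.xi puts mean volume, time trend and consumption factors under this one primary endpoint. On the volumes it says "These descriptive data will be pooled from AA-ORS and placebo arms". The trend is to be described by Lowess curves and tested with linear mixed models, and the factors by linear regression. No second population or sensitivity analysis is named.

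Three other provisions bear on the point:

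- Section C.iii (Discontinuation of Study Product Use and Withdrawal From the Study) says that when a participant chooses to stop study procedures, including the product, "this will be recorded as a study deviation and the reason will be clearly documented".
- The same section says of withdrawn children: "The data collected before withdrawal will be analyzed".
- The missing-data paragraph of C.xi plans no imputation but will examine "differential missingness or loss to follow-up by supplementation arm for the primary endpoints".

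**The concern.** The objective behind this endpoint is feasibility and a well-tolerated dose (C.ii, Objectives). Section C.iii (Study Approach) says the study will describe whether the product can feasibly be taken for two weeks. A population defined by having taken it for two weeks removes part of that answer.

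Dosing is ad libitum, so a child who takes a few spoonfuls on each of 14 days remains in the analysis. The children lost are those who stop. Section C.iii lists grounds for stopping that can be linked to refusal or poor tolerance (noncompliance, adverse events, weight loss) and others that need not be (ineligibility, protocol deviation, intercurrent illness).

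Table 7 in section D.i says the mean daily volume is to guide dosing in a future trial. An upward bias would carry into that choice. The trend and factor models would likewise describe only children who kept going.

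**Working it through.** **Plan figures.** The plan gives no precision or power figure for volume. Its sample size rests on safety: P(at least one event) = 1 − 0.9^30 = 0.958, which matches the 95.8% in Table 6. Section C.iii (Sampling Strategy) gives N = 66 and dropout of at most 10%. Since 0.10 × 66 = 6.6, at most 6 children stop within that ceiling. The ceiling covers all causes, so six low-intake stops is an upper case.

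**Effect on the mean.** All intakes below are assumptions. Let completers average C ml/day, k stoppers average L ml/day, and N = 66.

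All-dosed mean = [(66 − k)·C + k·L]/66. Per-protocol mean = C. Overstatement = C/mean − 1.

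| C | L | k = 1 | k = 3 | k = 6 |
|---|---|---|---|---|
| 180 | 20 | 177.6 (1.4%) | 172.7 (4.2%) | 165.5 (8.8%) |
| 180 | 100 | 178.8 (0.7%) | 176.4 (2.1%) | 172.7 (4.2%) |
| 120 | 60 | 119.1 (0.8%) | 117.3 (2.3%) | 114.5 (4.8%) |

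The differences run from 0.9 to 14.5 ml/day. If L = C, the overstatement is zero.

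**Mixed causes, k = 6.** Three children drink 20 ml to day 7 and then nothing (14-day mean 10). Three stop for unrelated reasons and would have stayed at 180.

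- Reference: (60·180 + 3·10 + 3·180)/66 = 172.3.
- Per-protocol: 180/172.3 − 1 = 4.5% too high.
- All-dosed, observed days: (60·180 + 3·20 + 3·180)/66 = 172.7, which is 0.3% too high.

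**What observed days cannot correct.** Six children drink 180 ml to day 7 and then nothing (14-day mean 90).

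- Reference: (60·180 + 6·90)/66 = 171.8.
- Per-protocol and observed-days analyses both give 180, which is 4.8% too high.
- Entering 0 ml after the stop gives 171.8, with no error.
- If those six would have gone on drinking 180 ml, the reference is 180 and zero-fill is 171.8/180 − 1 = 4.5% too low.

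**Trend.** Sixty children stay at 180 ml. Six fall in a straight line from 180 on day 1 to 20 on day 7 and then stop.

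- Completers: flat at 180 throughout.
- All-dosed daily means, days 1 to 7: 180, 177.6, 175.2, 172.7, 170.3, 167.9, 165.5.
- Observed days only, days 8 to 14: back to 180, because the six have gone. A least-squares line through the 14 daily means rises by 0.5 ml/day, a false recovery.
- Random-intercept mixed model on all observed days: about −0.3 ml/day.
- Zero-fill, days 8 to 14: 60·180/66 = 163.6. The line through the daily means falls by 1.3 ml/day.

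**Stopping rate.** This needs no intake assumption. Three of 66 is 4.5% (exact 95% CI 0.9% to 12.7%), and six of 66 is 9.1% (3.4% to 18.7%).

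**The case against.** The strongest reply is that this is a reasoned choice in a phase I pilot. The population is prespecified with a stated reason, and typical intake among children dosed for 14 days is a legitimate quantity when choosing a later dose. Volume has no arm comparison and no go/no-go threshold. Sampling error may also be larger than the bias: if the between-child SD were 40 to 80 ml (assumed), the 95% half-width with 60 children would be about 10 to 21 ml, and most of the differences above are smaller than that. This stands as far as size goes. It does not remove the mismatch, because the bias can only run one way if low drinkers are the ones who stop, and the completers' mean can be kept as a supporting result.

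A reader might infer more than the documents support:

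- *That the plan rules out an all-dosed analysis.* It does not. It names a primary population, which leaves room for others, and says in general that pre-withdrawal data will be analysed. But that sentence names no endpoint or population, and the intention-to-treat analyses already satisfy it. The fair statement is that no such analysis of volume is specified.
- *That low drinkers are excluded.* Only those who stop are.
- *That the plan contradicts itself by aiming at the full sample.* The parenthesis naming both arms reads most naturally as pooling over arms.
- *That stopping is concealed.* Reasons for stopping are documented, the by-arm missingness check would yield counts, and stoppers stay in the safety and acceptability analyses. A stopping rate would not be taken from the per-protocol set anyway. What is missing is a commitment to report stopping as a feasibility result. The check by arm also would not reveal bias in a pooled mean if low drinkers stopped equally often in both arms.
- *That moving to all dosed children settles the trend.* On observed days alone it can show a spurious recovery.

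**Conclusion.** The point holds at moderate strength. The plan conditions a feasibility endpoint on completion and specifies no analysis of it in all dosed children. The direction of bias in the mean is upward if stopping goes with low intake or refusal. Its size cannot be derived from the documents: over the assumed intakes it is about 1% to 9% with 1 to 6 of 66 stopping, and the top of that range needs every anticipated dropout to be a near-refuser. If stopping is unrelated to intake, the mean is unbiased. The trend and factor models describe completers only in any case. This is a worthwhile improvement rather than a flaw that would invalidate the study.

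**What to change.** In section C.xi:

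1. Make the intention-to-treat set already defined (at least one dose) the population for volume, trend and factors, using all observed bottle-days. Keep per-protocol as a sensitivity analysis.
2. Report the number of children stopping, with day and reason, overall and by arm, as a feasibility result.
3. For the trend, do not rely on Lowess curves or raw daily means of observed days alone. Fit the mixed model to all observed days. Also show the curve with 0 ml after a stop for refusal or noncompliance only, beside the completers' curve.

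A clarifying sentence in the discontinuation section that low intake of an offered dose is not noncompliance is optional; the fix does not depend on it.

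**Cost.** Mostly analysis-plan wording, since residual volumes and stop reasons are already collected. Separating refused from missed home doses needs one extra form item, answered by the caregiver. The mean may come out slightly lower and will mix completers with non-completers. Zero-fill understates intake if the child would have kept drinking, so it should stay a sensitivity analysis.

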**STUDY ENDPOINTS TO BE ANALYZED AND ANALYTICAL METHODOLOGY**

**Primary:** AEs and SAEs through 21 days of follow-up, and changes to dietary and digestive habits through day 14 of follow-up.

*For AEs and SAEs that occur within 21 days of enrollment, statistical comparisons will be made between the AA-ORS and the placebo solution groups using Fisher's exact test. Changes to feeding habits (normal, less frequent/less volume, more frequent/more volume), diarrhea (1–2, 3–4, 5–7, or 7+ events in 24 hours), and vomiting (none, 1, 2–5, > 6 events in 24 hours, or hospitalization) will be made using chi-square tests.*

**Primary:** Average daily product volume consumed through 14 days of follow-up, time trends in daily volume consumed, and factors that influence children's willingness and ability to ingest the product as intended.

*The average daily volume (and statistical distribution) of solution consumed by children over the 2-week period will be calculated. These descriptive data will be pooled from AA-ORS and placebo arms as the solutions are designed to taste the same. Lowess curves will be used to describe trends in volumes consumed, and linear mixed effects models will be used to test for an association between day of follow-up and product volume consumed. We will use linear regression to identify factors (e.g., child weight, length, and age) associated with a child's average daily intake.*

**Secondary:** Key factors that influence caregivers' willingness to have the product used by their children, and their perception of their children's response to its consumption.

*These qualitative analyses will use ATLAS.ti software to identify and group key themes and topics from IDI notes.*

**Exploratory:** Average plasma/serum concentrations of metabolic, gut dysfunction, systemic inflammation, and micronutrient biomarkers at baseline and day 15 of follow-up.

*Metabolic, EED, systemic inflammation, and micronutrient marker data collected at baseline will be pooled across intervention groups and used to generate descriptive statistics for the study population. The same descriptive statistics will be generated for day 15 of follow-up. Paired student's t test will be used to compare these continuous parameters between baseline and day 15 of follow-up.*

*Unpaired student's t test will be used to compare these continuous parameters between the two study groups at day 22. A difference with  $P < 0.05$  will be considered statistically significant. However, there is limited statistical power to make such comparisons between study groups for biomarker outcomes.*

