#### ii. Aims of proposed research study

We propose to conduct a small pediatric pilot study to determine patient safety, feasible product volume (trends in dosage consumed over 14 days, etc.), and caregiver (i.e., parent or legally acceptable representative) acceptability of AA-ORS in the target population at risk for EED. To assess the product's safety, we will randomize children to receive active product or placebo and compare the rate of adverse events (AEs) in the two groups. We will also assess the extent to which the product might meet the needs of the target population and setting. Results from this study will be used to inform:

- a) The design of a randomized controlled trial to test the efficacy of AA-ORS for treating pediatric EED.
- b) Future EED product development efforts.
- c) Program implementation strategies for EED interventions.

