#### Objectives

**PRIMARY OBJECTIVE:** To determine the safety of AA-ORS among children with mild to moderate stunting, administered as a daily dose over 2 weeks, ad libitum up to 237 ml in 3 hours.

*Safety assessment in children will compare adverse event (AE) and serious adverse event (SAE) rates and changes to dietary and digestive habits between children receiving AA-ORS versus an inactive placebo solution containing no amino acids.*

**PRIMARY OBJECTIVE:** To determine the feasibility and well-tolerated dose of AA-ORS among children with mild to moderate growth stunting administered as a daily dose over 2 weeks, ad libitum up to 237 ml in 3 hours.

*User preferences among children include average daily volume consumed over 14 days, trends in volume consumed, and factors that influence children's willingness and ability to ingest the product as intended.*

**SECONDARY OBJECTIVE:** To determine the perceptions among caregivers on the use and acceptability of this product as a potential intervention for EED.

*Acceptability by caregivers includes factors that influence their willingness to have the product used by their children and their perception of their child's response to its consumption.*

**EXPLORATORY OBJECTIVE:** To determine the impact of AA-ORS on gut dysfunction, metabolism, gut and systemic inflammation, and micronutrient status.

*Impact of AA-ORS on gut dysfunction, systemic inflammation, and micronutrient status will be assessed by comparing non-invasive biomarker levels in blood samples collected following the intervention. These biomarkers will be assessed in both groups at baseline in order to have setting-specific descriptive data with which to power a future EED efficacy trial.*

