#### iv. Control or comparison group use

Controls will be children from the same patient population as those receiving AA-ORS. These children will receive a placebo solution containing all the non-amino acid and non-electrolyte components of the AA-ORS and therefore will be able to contribute useful information regarding the feasible dose of the solution. This placebo solution is produced by the manufacturer of the AA-ORS for the purpose of clinical studies. Because these children will not be receiving the amino acids, they will provide the background rate of AEs (and morbidity experience) of children in this population, allowing for the detection of an unusually high event rate in the AA-ORS group, should it arise.

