#### *Definition of Adverse Event (AE)*

An adverse event (AE) is any untoward medical occurrence in a participant after administration of the study product and that does not necessarily have a causal relationship with the study product. An AE can therefore be any unfavorable and unintended signs (including abnormal laboratory findings), symptoms, physical examinations, or disease temporally associated with the use of the study product, whether related to the study product or not. This definition includes exacerbations of pre-existing conditions. Stable pre-existing conditions that do not change in nature or severity during the study are not considered AEs; however, these should be reported as part of the medical history.

**Solicited AEs** are pre-specified adverse events that are actively monitored by study staff during the full 21 days of follow-up. Personal communication with the study product manufacturer indicated that no adverse events have been found to be associated with the AA-ORS in adult studies or in the small study (n=5) featuring children with short bowel syndrome.

For this study, solicited AEs will be assessed by study nurse 30 minutes after the first administration (in person), and then by phone on days 4, 7, 14, and 21.

The following specific solicited adverse events will be monitored for this trial:

- *Vomiting.*
- *Diarrhea.*
- *Fever.*
- *Constipation.*
- *Lethargy.*
- *Irritability/restlessness.*
- *Allergic reactions:* sudden swelling of the face or throat, itching, and rash.
- *Other reactions:* fits (convulsions/seizures); gas, abdominal cramps, or stomach pain; weight loss.

Changes in the severity of an AE (e.g., diarrhea) will be documented to allow an assessment of the duration of the event at each level of severity to be performed. AEs characterized as intermittent require documentation of onset and duration of each episode.

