### i. Risks to research study participants/groups

#### *Risk Considerations*

The proposed study is expected to be of minimal risk as the study AA-ORS is a medical food product regulated by the US FDA. As a result, we do not anticipate any adverse events for this study related to the administration of AA-ORS, but we will include a control arm in order to better assess the safety of this product in children with mild-moderate stunting. Children with mild to moderate stunting are at increased risk for morbidity and mortality, so we anticipate that participants may report diarrhea or respiratory infections at high rates, regardless of receipt of active AA-ORS or placebo. While there is mounting evidence that microbiome immaturity contributes to growth deficits in LRS, any changes to the microbiome composition and diversity from provision of AA-ORS are likely to be transient, based upon previous observations among infants and children provided probiotic-supplemented formula or ready-to-use supplementary food (43, 44).

This study involves blood specimen collection. The collection of these samples involves venipuncture, which may cause discomfort, pain, introduction of infection, bleeding, fainting, or bruising. Precautions will be taken to avoid introduction of infection by disinfecting the site of venipuncture and using sterile equipment. The risk of bleeding and bruising will be minimized by immediate application of pressure after venipuncture. The child will be restrained appropriately by the caregiver to prevent kicking of the phlebotomist. A thorough description of potential risk considerations and mitigation strategies is outlined in Table 7.

**Table 7.** Known risks and mitigation strategies for SAFE study participants.

Potential risk to participant	Concern	Study design feature intended to minimize risk	Rationale for the necessity of exposing participants to risk

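### The Fisher test for AEs has no stated unit or outcome, and no planned analysis uses the episode counts, durations or grades the trial records

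*Combined protocol and SAP*

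**What the plan says.** **The aim is a rate comparison.** Section C.ii says the trial will "compare the rate of adverse events (AEs) in the two groups". The first primary objective says the safety assessment "will compare adverse event (AE) and serious adverse event (SAE) rates and changes to dietary and digestive habits between children receiving AA-ORS versus" placebo. Section C.iv gives the control arm the purpose of "allowing for the detection of an unusually high event rate in the AA-ORS group, should it arise".

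**The data go beyond yes/no.** Under Definition of Adverse Event (Section C.x), changes in severity "will be documented to allow an assessment of the duration of the event at each level of severity to be performed". Onset and duration of each episode must be recorded for AEs classed as intermittent. Severity has four levels, and Appendix 8 gives a grading table for solicited AEs.

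**The analysis.** In Section C.xi, for AEs and SAEs within 21 days of enrollment, "statistical comparisons will be made between the AA-ORS and the placebo solution groups using" Fisher's exact test. The unit and the form of the outcome (any AE, by type, by grade) are not given. The same paragraph adds chi-square tests on feeding habits and on frequency categories: "diarrhea (1–2, 3–4, 5–7, or 7+ events in 24 hours), and vomiting (none, 1, 2–5, > 6 events in 24 hours, or hospitalization". These fall under the dietary and digestive part of the endpoint, which runs through day 14.

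**Background illness.** Under Risk Considerations (Section D.i), "we anticipate that participants may report diarrhea or respiratory infections at high rates" whichever product they receive. No figure is attached.

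**The concern.** A rate is events per child or per unit of time. A per-child yes/no table answers a different question: how many children had at least one event. On that table, a child with one mild day of fever and a child with three severe episodes count the same. If most children have some AE in three weeks, a product that makes episodes more frequent, longer or worse may barely change the share with any AE.

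The plan also states a purpose for its duration-by-severity records and then plans no analysis that serves it. With the unit unstated, an analyst could tabulate events instead of children. That would break the independence Fisher's test needs, since one child can contribute several episodes.

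At stake is the comparative part of a primary safety endpoint, whose results are meant to inform an efficacy trial.

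**Working it through.** **Inputs from the plan.** 33 children per arm; dropout up to 10%, so 33 × 0.9 = 29.7, about 30 evaluable; AE follow-up 21 days. The 0.05 level appears only with the biomarker t tests. I assume it applies here, two-sided and unadjusted.

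**The plan's own figure.** Table 6: P(at least one AE) = 1 − (1 − 0.10)^30 = 1 − 0.042 = 95.8%. This reproduces. It is the chance of seeing an event in one arm, not power to compare arms; the plan gives no between-arm power.

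**Fisher per child, exact enumeration.** Power is the sum of the products of the two binomial probabilities over all tables with P ≤ 0.05. At 33 per arm, roughly 80% power needs 10% v 42%, 30% v 66%, 50% v 85% or 70% v 97%. The highest power attainable, when every AA-ORS child has an AE, is:

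| Placebo children with any AE (assumed) | 33 per arm | 30 per arm |
|---|---|---|
| 80% | 67% | 57% |
| 85% | 37% | 29% |
| 90% | 11% | 7% |

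**Doubled episodes.** Counts per child are assumed negative binomial with mean m and dispersion parameter k, so P(any AE) = 1 − [k/(k + m)]^k. For m = 1.5, k = 2: 1 − (2/3.5)² = 67%. For m = 3: 1 − (2/5)² = 84%. Power from 20,000 simulated trials per row, 33 per arm:

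| Mean episodes | k | Any AE, placebo v AA-ORS | Fisher on any AE | Rank-sum on counts |
|---|---|---|---|---|
| 1.5 to 3 | 2 | 67% v 84% | 25% | 72% |
| 2 to 4 | 2 | 75% v 89% | 21% | 77% |
| 1.5 to 3 | 1 | 60% v 75% | 18% | 51% |
| 0.5 to 1 | 2 | 36% v 56% | 31% | 45% |
| 0.5 to 1 | 1 | 33% v 50% | 23% | 35% |

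With no true difference, the rank-sum test rejected in about 5% of trials and Fisher in about 3%, so the gain is not bought with excess false positives.

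**Check with an overdispersed Poisson rate ratio, doubled rate, k = 1.** With 50% of placebo children affected: Fisher 22%, rate ratio 54%. With 30%: 21% and 37%. With 10%: 8% and 8%. The rank-sum test reaches about 15% in that last case, still low; with so few repeat episodes, most of the difference reflects Fisher's conservatism rather than information in the counts.

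**The case against.** **The paragraph does contain other between-arm tests.** This stands. Diarrhea and vomiting are solicited AEs, and their frequency categories carry some intensity. A reader might infer that Fisher is the only between-arm look at AEs; the documents do not support that. But the chi-square tests use events per 24 hours, sit under an endpoint ending at day 14, ignore category order, and leave out fever, lethargy, irritability, allergic reactions and all unsolicited AEs, including respiratory infections.

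**Yes/no per child is an inference.** This also stands. It is the natural reading, but the plan does not say it, and Fisher's test extends to larger tables such as worst grade. The supportable defect is the missing definition.

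**The ceiling is assumed.** A reader might infer that the plan expects saturation. It says only that rates may be high. The ceiling needs about 80% or more of placebo children with the analysed outcome, and the sample-size section frames safety by type of event at 10%, where no ceiling exists. The loss of power at 33% to 75% background does not depend on it.

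**The data are imperfect.** Per-episode onset and duration are required only for intermittent AEs, and counts rest on caregiver recall between calls on days 4, 7, 14 and 21. The simulations treat counts as error-free.

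**This is a pilot with other safeguards.** An independent monitor confirms severity and relatedness, and a DSMB reviews safety. It would go too far to say that more frequent or worse events would pass unnoticed. The point concerns the planned comparison.

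**Fisher's test itself is valid.** Replacing it with a less conservative exact test is a preference, not a correction.

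**Conclusion.** The point holds in two parts. First, the unit and outcome of the primary AE test are undefined. Second, no planned analysis uses episode counts, duration or toxicity grade, although the aim is stated as a rate comparison and the data are collected for such use.

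The size depends on the background. With a mean of 1.5 to 2 episodes per placebo child, a doubling would be detected with about 18–25% power by Fisher on any AE against 51–77% by a rank-sum test on counts. With a mean of 0.5 it is 23–31% against 35–45%. For types affecting about 10% of children, both are weak and counts add little. If 80% or more of placebo children have any AE, Fisher on that outcome cannot reach 80% power at all.

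These figures rest on assumed negative binomial counts, a true doubling, 33 evaluable children per arm and an unadjusted two-sided 0.05. The Benjamini-Hochberg adjustment would generally lower power for either test. This is a worthwhile, cheap improvement to the analysis plan; it does not make the planned tests invalid when Fisher's is run per child.

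**What to change.** In Section C.xi, first primary endpoint:

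1. State that Fisher's exact test is per child, and keep it for SAEs and for each AE type.
2. Add one pre-specified between-arm comparison of total AE episodes per child through day 21: a negative binomial or overdispersed Poisson model with follow-up days as offset, reporting the rate ratio and 95% CI, with a permutation or rank-sum p-value as a check. The offset allows for children who leave early.
3. Add a between-arm comparison of worst grade per child by an ordered (rank-sum) test.
4. Say how an episode is counted, including AEs not classed as intermittent.

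Cost: plan wording and a little programming, with no new data. The downsides are reliance on caregiver recall between calls and one or two more tests within the Benjamini-Hochberg family.
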